#### **6.4. Study Intervention Compliance**

Participant compliance with study intervention will be assessed at each visit during the treatment period by counting returned tablets.

A participant will be considered noncompliant if they miss more than 20% of the prescribed doses of study intervention during the study, unless study intervention is withheld for safety reasons. Similarly, a participant will be considered significantly noncompliant if they are judged by the investigator to have intentionally or repeatedly taken 20% or more than prescribed amount of study intervention during the study.

If a participant's study intervention intake is not according to the protocol, the investigator will take the necessary measures to ensure future adherence to the protocol. If necessary, the participant may be discontinued from study intervention by the investigator or medical monitor (Section 7, Discontinuation of Study Intervention and Participation Discontinuation/Withdrawal).

Study intervention compliance will be further detailed in the statistical analysis plan (SAP).

#### **6.5. Dose Modification**

This section is not applicable to this study.

#### **6.6. Continued Access to Study Intervention After the End of the Study**

Participants will be instructed that study intervention will not be made available to them after they have completed/discontinued study intervention and that they should return to their primary physician to determine standard of care.

#### **6.7. Treatment of Overdose**

For this study, any study intervention of JNJ-77242113 CCI greater than the highest dose at a single day will be considered an overdose. The sponsor does not recommend specific treatment for an overdose.

Decisions regarding study intervention interruptions will be made by the investigator in consultation with the medical monitor based on the clinical evaluation of the participant.

In the event of an overdose, the investigator or treating physician should:

- Contact the Medical Monitor immediately.
- Evaluate the participant to determine, in consultation with the Medical Monitor, whether study intervention should be interrupted.
- Closely monitor the participant for adverse event (AE)/SAE and laboratory abnormalities.
- Obtain a plasma sample for PK analysis if requested by the Medical Monitor (determined on a case-by-case basis).

- Document the quantity of the excess dose as well as the duration of the overdosing in the electronic case report form (eCRF).

## 6.8. Concomitant Therapy

Modification of an effective preexisting therapy should not be made for the explicit purpose of entering a participant into the study. Concomitant therapies must be recorded throughout the study beginning with start of the first administration of study intervention to 4 weeks after the last administration of study intervention.

All therapies (prescription or over-the-counter medications) different from the study intervention must be recorded in the eCRF. Every effort should be made to keep participants on stable concomitant therapies. If a medication is temporarily discontinued because of abnormal laboratory values, side effects, concurrent illness, or the performance of a procedure, the change and reason for it should be clearly documented in the participant's medical records.

The dosing regimen of histamine type-2 (H2) receptor antagonists/blockers (including but not limited to famotidine, cimetidine, nizatidine, ranitidine) or antacids (including but not limited to aluminum hydroxide, calcium carbonate, magnesium hydroxide, Gaviscon, Gelusil, Maalox, Mylanta, Roloids, Pepto-Bismol), must be staggered with the evening dose of the study intervention. If once daily dosing, the H2 blockers/antacid must be administered in the morning. If twice daily dosing, the first dose of H2 blockers/antacid must be administered in the morning and the second dose must be administered 5 hours before study intervention).

Any questions regarding treatment with concomitant therapy during the study should be directed to the medical monitor.

## Prohibited Therapy

All experimental therapies or new investigational interventions (except for JNJ-77242113), including therapies for psoriasis or other conditions, must be discontinued prior to the first administration of study intervention per exclusion criteria (Section 5.2, Exclusion Criteria) and remain prohibited during the study. For guidance regarding the COVID-19 vaccine see Section 10.7, Appendix 7: Guidance on Study Conduct During the COVID-19 Pandemic.

Use of proton pump inhibitors (including but not limited to omeprazole, esomeprazole, lansoprazole, rabeprazole, pantoprazole, dexlansoprazole, or Zegerid) is prohibited during the study, per exclusion criterion 17 (Section 5.2, Exclusion Criteria).

If a prohibited therapy is administered during the study, the medical monitor should be notified, and the participant may be required to discontinue from the study treatment per medical monitor's discretion. If a prohibited therapy is initiated during the follow-up period, the participant should still complete his or her final study visit, and the medication should be recorded as a concomitant therapy.

The sponsor must be notified in advance (or as soon as possible thereafter) of any instances in which prohibited therapies are administered.

## **Psoriasis Concomitant Therapy**

### ***Topical Therapy***

Topical therapies that could affect psoriasis or the PASI/IGA evaluation (eg, corticosteroids, tar, anthralin, calcipotriene, tazarotene, methoxsalen, pimecrolimus, tacrolimus, and traditional Taiwanese, Korean, or Chinese medicines) are not permitted during the study for the treatment of psoriasis or for use on the hands and feet for any reason. The only allowable concomitant treatments throughout the study are shampoos (containing salicylic acid only) and topical moisturizers. Participants should not use these topical agents (shampoos and moisturizers) the day of a study visit, prior to assessments. Nonmedicated shampoos may be used on the day of the study visit.

### ***Phototherapy or Systemic Therapy***

The use of phototherapy or systemic medications that could affect psoriasis or the PASI/IGA evaluation is not permitted at any time during the study. These medications include, but are not limited to, those targeting IL-12/23, IL-17, IL-17 receptor, or IL-23 (including but not limited to ustekinumab, guselkumab, tildrakizumab [MK3222], secukinumab, risankizumab [BI-655066], ixekizumab [LY2439821], or brodalumab [AMG827]), biologic therapy targeting TNF (including but not limited to adalimumab, infliximab, or etanercept), agents that deplete or modulate B cells (including but not limited to rituximab, belimumab, or alemtuzumab), alpha-4 integrin antagonists (including but not limited to natalizumab), T cell modulators (including but not limited to abatacept or visilizumab), JAK inhibitors (including but not limited to TYK2 inhibitors), PDE4 inhibitors (including but not limited to apremilast), other conventional systemic immunosuppressants (including but not limited to methotrexate, sulfasalazine, azathioprine, cyclosporine, 6-thioguanine, mercaptopurine, mycophenolate mofetil, gold, or tacrolimus), oral and injectable (IV, intramuscular, or intralesional) corticosteroids, any other conventional systemic therapies that could affect psoriasis or the PASI/IGA evaluation (including but not limited to acitretin or other retinoids, 1,25-dihydroxy vitamin D3 and analogues, lithium, antimalarials, herbal treatments, or traditional Taiwanese, Korean, or Chinese medicines), and any other biological agent or other systemic medication that could affect psoriasis or the PASI/IGA evaluation.

The use of systemic corticosteroids for indications other than psoriasis should be limited to situations for which, in the opinion of the treating physician, there are no adequate alternatives. They should be used on a short-term basis, preferably for  $\leq 2$  weeks. Longer term use of corticosteroids should be discussed with the medical monitor or designee and may require discontinuation of study intervention. Inhaled, otic, ocular, nasal, or other routes of mucosal delivery of corticosteroids are allowed throughout the study.

### **6.8.1. Vaccinations (Including COVID-19)**

When considering use of locally approved non-live vaccines (including emergency use-authorized COVID-19 vaccines) in study participants, follow applicable local vaccine labeling, guidelines, and standards-of-care for participants receiving immune-targeted therapy.

## 7. DISCONTINUATION OF STUDY INTERVENTION AND PARTICIPANT DISCONTINUATION/WITHDRAWAL

### 7.1. Discontinuation of Study Intervention

A participant's study intervention must be discontinued if:

- The participant withdraws consent to receive study intervention.
- The investigator believes that for safety reasons or tolerability reasons (eg, AE) it is in the best interest of the participant to discontinue study intervention.
- The participant meets the Sampson criteria for anaphylaxis following study intervention administration (Section 10.10, Appendix 10: Criteria for Assessing Potential Cases of Anaphylaxis) (Sampson 2006).
- The participant has a reaction resulting in myalgia and/or arthralgia with fever and/or rash (suggestive of serum sickness and not representative of signs and symptoms of other recognized clinical syndromes) occurring 1 to 14 days after an administration of study intervention. These may be accompanied by other events including pruritus, facial, hand, or lip edema, dysphagia, urticaria, sore throat, and/or headache.
- The participant becomes pregnant or plans a pregnancy during the study period (Section 10.5, Appendix 5, Contraceptive and Barrier Guidance).
- The initiation of protocol-prohibited medications, treatments, or interventions (outlined in Section 6.8, Concomitant Therapy) that have an impact on psoriasis efficacy evaluations at the discretion of the medical monitor.
- The participant has a malignancy including squamous cell skin cancer. Consideration may be given to allow participants, who develop  $\leq 2$  basal cell skin cancers and who are adequately treated with no evidence of residual disease, to continue to receive study intervention.
- The participant develops a systemic opportunistic infection during the study period.
- The participant develops a recurrent or chronic serious infection during the study period.
- The participant meets ANY of the following TB related conditions:
  - A diagnosis of active TB is made.
  - A participant has symptoms suggestive of active TB based on follow-up assessment questions and/or physical examination or has had recent close contact with a person with active TB and cannot or will not continue to undergo additional evaluation.
  - A participant undergoing evaluation has chest imaging with evidence of current active TB and/or a positive IGRA test result, unless active TB can be ruled out and appropriate treatment for latent TB can be initiated prior to the next administration of study intervention and continued to completion. Indeterminate/borderline results should be handled as outlined in Section 8.2.8, Tuberculosis Evaluations.
  - A participant receiving treatment for latent TB discontinues this treatment prematurely or is noncompliant with the therapy.
- The participant is unable to adhere to the study visit schedule or comply with protocol requirements.

- The participant has a possible Hy's Law case, as defined by the occurrence of alanine aminotransferase (ALT) or aspartate aminotransferase (AST)  $\geq 3 \times \text{ULN}$ , together with total bilirubin  $\geq 2 \times \text{ULN}$  or International Normalized Ratio (INR)  $> 1.5$  (if measured) without an identifiable cause (Section 10.6, Appendix 6: Liver Safety: Suggested Actions and Follow-up Assessments).
- The participant has his/her treatment assignment unblinded by the investigator.
- Sponsor decision.

Discontinuation of a participant's study intervention must be strongly considered if the participant develops a serious infection, including but not limited to sepsis or pneumonia. In addition, any serious infection should be discussed with the medical monitor or designee, and study intervention should be withheld until the clinical assessment is complete.

Discontinuation of a participant's study intervention should be considered for participants with any type of suicidal ideation or behavior, or any self-injurious behavior, who are deemed to be at risk by the investigator. Discussion of such participants with the medical monitor or designee is required.

For participants who report Suicidal Ideation with Intention to Act ("Ideation level 4"), suicidal ideation with specific plan and intent ("Ideation level 5"), suicidal behavior (actual suicide attempt, interrupted suicide attempt, aborted suicide attempt, or preparatory behaviors for making a suicide attempt) or any self-injurious behavior on a post-baseline C-SSRS assessment, the investigator risk assessment must be based upon evaluation by a mental health professional (Section 10.9, Appendix 9: Columbia Suicide Severity Rating Scale).

Participants who decide to discontinue study intervention administration for reasons other than those outlined above must be interviewed by the investigator to determine if a specific reason for discontinuing study intervention can be identified. Participants should be explicitly asked about the possible contribution of AEs to their decision to discontinue study intervention; investigators should confirm that any AE information elicited has been documented. If a participant elects to discontinue study intervention due to an AE, the event should be recorded as the reason for study intervention discontinuation, even if the investigator's assessment is that the AE would not require study intervention discontinuation. The reason for study intervention discontinuation must be documented in the eCRF and in source documents. Study intervention assigned to a participant who discontinues may not be assigned to another participant.

A participant will not be automatically withdrawn from the study if they must discontinue treatment before the end of the treatment regimen. Participants who discontinue study intervention but do not terminate study participation will continue to return for protocol-specified procedures and evaluations for approximately 4 weeks following the last administration of study intervention. Participants who terminate study intervention early should return for an early termination visit as soon as possible after discontinuing study intervention and return for the final follow-up visit approximately 4 weeks after their last administration of study intervention. More details will be provided in the eCRF completion guidelines.

All procedures and evaluations must be conducted prior to a participant's withdrawal of consent.

## **7.2. Participant Discontinuation/Withdrawal From the Study**

A participant will be withdrawn from the study for any of the following reasons:

- Lost to follow-up
- Withdrawal of consent
- The participant is not in compliance with requirements of the study, including prohibitions and restrictions
- Death

When a participant withdraws before study completion, the reason for withdrawal is to be documented in the eCRF and in the source document. If the reason for withdrawal from the study is withdrawal of consent then no additional assessments are allowed.

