#### 5.3.2.2.2. Supplementary Estimand 2 (Treatment Policy Estimand):

This supplementary estimand has the same components as the primary estimand, except for the strategies used for ICEs 1-3.

**Treatment policy strategy:** assess the treatment effect regardless of whether or not intercurrent events had occurred. Under the treatment policy strategy, observed data collected after ICEs will be used in analysis.

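### Protocol 7.2 requires withdrawal from the study for non-compliance, contradicts 6.4, 6.8 and 7.1, and may cost Week 16 and safety data that the plan intends to collect

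*Protocol*

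**What the plan says.** Protocol 7.2 opens its list with "A participant will be withdrawn from the study for any of the following reasons". Beside loss to follow-up, withdrawal of consent and death stands "The participant is not in compliance with requirements of the study, including prohibitions and restrictions".

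Other sections deal with the same conduct as follows.

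- **Protocol 6.4** defines poor adherence: "A participant will be considered noncompliant if they miss more than 20% of the prescribed doses of study intervention during the study", except when drug is withheld for safety. The investigator first acts to improve adherence, and then: "If necessary, the participant may be discontinued from study intervention by the investigator or medical monitor".
- **Protocol 6.8, Prohibited Therapy**, says that a participant who takes a prohibited therapy may have to stop study treatment, at the medical monitor's discretion. For the follow-up period it adds: "If a prohibited therapy is initiated during the follow-up period, the participant should still complete his or her final study visit".
- **Protocol 7.1** lists inability to comply with the protocol, and prohibited therapy that affects the efficacy evaluations, as reasons to stop study intervention. It then says: "A participant will not be automatically withdrawn from the study if they must discontinue treatment before the end of the treatment regimen".

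On the analysis side, SAP 5.3.2.1 and 5.3.3.1 treat ICE 2 (prohibited therapy that could improve psoriasis) as non-response. For ICE 3 (stopping drug for reasons other than ICE 1) they use observed data, and they score a missing Week 16 result as non-response. For Supplementary Estimand 2, SAP 5.3.2.2.2 says: "Under the treatment policy strategy, observed data collected after ICEs will be used in analysis". SAP Appendix 4 lists meeting withdrawal criteria without being withdrawn as a category of major deviation.

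**The concern.** One act, such as missing a quarter of the doses or taking a barred drug, has two prescribed outcomes. Under 7.2 the participant leaves the study. Under 6.4, 6.8 and 7.1 the participant at most leaves study drug. A site that keeps the participant can be charged with a major deviation, and a site that withdraws the participant departs from 6.8. Sites will resolve this differently, so the pattern of missing data will depend partly on which section a site reads.

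At stake are Week 16 PASI values that could have been observed and would instead be scored as non-response, observed data for the treatment-policy supplementary estimand, and possibly scheduled safety follow-up.

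**Working it through.** **1. Which participants lose something under 7.2**

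Inputs: follow-up ends about 4 weeks (28 days) after the last dose (Protocol 7.1 and the early-termination footnote to the Schedule of Activities). The SAP 5.1.1 window for Week 16 is Days 99 to 126. Early-termination and final follow-up visits are mapped into the windows.

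The last follow-up visit reaches the Week 16 window only if last dose + 28 ≥ 99, so the last dose must fall on about Day 71 or later (99 − 28 = 71).

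| Participant | If 7.2 is not applied | If 7.2 is applied |
|---|---|---|
| Poor adherer left on drug under 6.4 | Week 16 PASI can be observed | May be missing, then non-responder |
| User of a prohibited drug that does not improve psoriasis (6.8 bars proton pump inhibitors, for example), left on drug | Not ICE 2; Week 16 PASI can be observed | May be missing, then non-responder |
| Non-compliant, ICE 3, stops at about Day 71 or later | A PASI can fall in the Week 16 window | May be missing, then non-responder |
| Non-compliant, ICE 3, stops before about Day 71 | No Week 16 value, because 7.1 has ended follow-up | No change |
| ICE 2, primary analysis | Non-responder | No change |
| ICE 2, Supplementary Estimand 2 | Observed PASI used where available | Observed PASI may be lost and imputed |

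A participant withdrawn under 7.2 while still on drug also stops drug, for a reason other than ICE 1. That is ICE 3, for which the SAP asks for observed data.

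**2. The plan's own power figure**

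Inputs (Protocol 9.2, SAP 3): 20 placebo and 30 per active dose, two-sided alpha 0.10 (z = 1.645), a 35-point difference, placebo 5% to 10%, at least 90% power.

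For 40% versus 5%:

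- Pooled rate = (20 × 0.05 + 30 × 0.40)/50 = 0.26. SE0 = √[0.26 × 0.74 × (1/20 + 1/30)] = 0.1266.
- SE1 = √[0.05 × 0.95/20 + 0.40 × 0.60/30] = 0.1019.
- Pooled Z-test: Φ[(0.35 − 1.645 × 0.1266)/0.1019] = 91.8%.
- Unpooled Z-test: Φ[0.35/0.1019 − 1.645] = 96.3%.

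For 45% versus 10% the same formulas give 87.6% and 92.7%. Exact enumeration of the pooled test gives 94.8% and 90.2%. The stated figure therefore reproduces over the range with the unpooled or exact version, and at the 5% placebo rate with the pooled one.

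**3. Illustration of loss**

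The documents give no non-compliance rate. Assume that a share w of each arm is withdrawn under this bullet and scored as non-response, that response is unrelated to withdrawal, and that none of these participants would be non-responders anyway. Both rates are multiplied by (1 − w). At w = 10% the difference is 0.90 × 35 = 31.5 points.

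| w | Difference (points) | 40% v 5%, pooled / unpooled | 45% v 10%, pooled / unpooled |
|---|---|---|---|
| 0 | 35.0 | 91.8% / 96.3% | 87.6% / 92.7% |
| 5% | 33.3 | 89.8% / 95.2% | 85.1% / 90.9% |
| 10% | 31.5 | 87.5% / 93.7% | 82.3% / 88.8% |
| 20% | 28.0 | 81.9% / 89.9% | 75.9% / 83.7% |

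One responder lost from an active arm moves its rate by 1/30 = 3.3 points.

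**The case against.** The strongest reply is that little need be lost in practice. Protocol 7.2 stops assessments for one reason only: "If the reason for withdrawal from the study is withdrawal of consent then no additional assessments are allowed". Anyone withdrawn has also stopped drug, and 7.1 and the Schedule of Activities footnote ask those who stop early to return for an early-termination visit and a 4-week visit. PASI is recorded at both and can be mapped to Week 16. Section 8.7 requests a final-visit sample from withdrawn participants, 8.2 follows abnormalities that persist at early withdrawal, and 8.3.1 keeps serious adverse event reporting to 4 weeks. All of this stands, so the loss is a risk and not a certainty. It does not remove the risk: 7.2 names no visit for someone withdrawn for non-compliance, and 7.1 makes continued visits conditional on not having ended study participation.

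It can also be said that 6.4 refers to the whole of Section 7, so escalation to withdrawal is contemplated, and that 7.2 does not name stopping drug as a trigger, so the 7.1 sentence is not itself a contradiction. Both are fair. The conflict is that the same conduct has different consequences in the two lists, and that 6.8 keeps participants whom 7.2 removes.

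A reader might infer more: that every visit ends on the day non-compliance is found, that Supplementary Estimand 2 becomes wholly imputed for ICE 2, or that the primary estimand loses data it needs for prohibited-therapy users. The documents do not support these. The first two ignore the provisions above, and the third ignores the composite strategy. Nor do the SAP's 80% per-protocol cut and compliance categories require retention, since both can be calculated for participants who have left.

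**Conclusion.** The contradiction is real and stands in current text. Read literally, 7.2 works against the plan's own estimands, because it can turn a Week 16 PASI that would have been observed into a missing value scored as non-response. The effect on the primary analysis is confined to non-compliant participants still on drug and to non-compliant ICE 3 participants who stop at about Day 71 or later. Beyond that, Supplementary Estimand 2 may lose data after ICE 2, and scheduled safety follow-up may be lost.

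The size cannot be established from the documents. The power figures are illustrations that depend on the assumed share withdrawn and on the version of the Z-test, which the plan does not specify. If poor adherers respond less often than others, the loss is smaller than shown. The case for a change rests on the inconsistent text, not on these figures. It should be corrected, but it does not put the trial's design in question.

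**What to change.** In one protocol amendment:

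1. Remove the non-compliance bullet from 7.2 as a mandatory reason for leaving the study, so that non-compliance alone ends neither participation nor data collection.
2. State in 7.2 that scheduled efficacy and safety assessments continue for these participants, and align the wording with 6.4, 6.8 and 7.1.
3. Reconcile that statement with the limit of about 4 weeks after the last dose in 7.1 and the Schedule of Activities footnote. Changing 7.2 alone would create a new conflict for anyone who stops drug early, and would not recover Week 16 data for those who stop before about Day 71.

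When study intervention should be stopped is for the sponsor to settle, and this point takes no position on it. The cost is text in three places. For participants still on drug it uses only visits already scheduled. Any longer follow-up after stopping drug is a separate choice under item 3.
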